The PI will oversee recruitment of potential participants, collection and storage of study data, regulatory deadlines and data analysis. This will be accomplished primarily through a standing weekly meeting with research team members. The PI will also meet individually with the study coordinator weekly or as needed to discuss recruitment and any safety issues related to data collection.
- 2 * **Describe the facilities where research procedures are conducted:**
All patient's will be consented at the VA Medical Center. They will also complete neurocognitive testing, questionnaires, and phlebotomy at the VA Medical Center. Participants will be escorted to the vascular lab at the University of Maryland Medical Center to complete imaging and walking and balance assessments. Patient's recruited from the University of Maryland Medical Center will be escorted to the VA Medical Center for consenting, neurocognitive testing, questionnaires, and phlebotomy.

For the purpose of the additional follow-up planned; patients will undergo ultrasound testing, physical function testing and questionnaires at the University of Maryland Medical Center vascular lab.
- 3 * **Describe the availability of medical and/or psychological resources that subjects might need as a result of anticipated consequences of the human research:**
All efforts will be made to ensure subjects are seen safely and efficiently. Reasonable time will be allotted for each subject to complete testing. All procedures will be conducted by trained professionals in the areas of phlebotomy, neuropsychology, and vascular imaging. The PI is available by phone and pager at all times.
- 4 * **Describe the process to ensure that all persons assisting with the research are adequately informed about the protocol, the research procedures, and their duties and functions:**
The PI will speak with all research team members to discuss the study (purpose and procedures) and their role within the study. A standard of practice document will be completed and placed in the research office outlining all procedures of the study. Protocol and study related topics are discussed regularly at a weekly ACCOF conference with all team members.

ID: VIEW4DF83CB976400
Name: v2_Resources

View: v2_Sites Where Research Activities Will Be Conducted

Sites Where Research Activities Will Be Conducted

- 1 * **Is this study a:**
 Multi-Site
 Single Site

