Specific Aim 1 is to determine whether patients with asymptomatic carotid stenosis will differ in cognitive function compared to age-matched individuals without carotid stenosis but with similar vascular risk factors. The primary hypothesis is that in patients with asymptomatic carotid stenosis ($\geq 50\%$ diameter-reducing) who survive stroke-free for 2 years; the change in overall and domain-specific cognitive function will be significantly different compared to those without stenosis. The primary analysis of impact will be the overall and domain-specific cognitive change score at 2 years, with the initial score at recruitment serving as the baseline.

Patient recruitment

Eligible patients are defined as having asymptomatic $\geq 50\%$ diameter reducing carotid stenosis. Asymptomatic status in patients will be confirmed by a history, physical examination, and numeric NIH Stroke Scale96 as defined in prior NIH carotid trials1-4. While asymptomatic patients with diameter stenosis $\geq 60\%$ benefit from revascularization2, that benefit is reduced when compared to symptomatic patients1, 4. Most centers including

ours, follow the common practice of operating on symptomatic patients with stenosis, but only consider revascularization for asymptomatic patients when the stenosis is >80%^{45, 46}. In this standard of care approach, asymptomatic patients with moderate carotid stenosis (50-80%) are treated medically and followed with annual screening studies to monitor for disease progression. Once a decision has been made that they do not require revascularization, these patients will be recruited to our proposed study. The decision as to whether a subject is appropriate to be followed with medical management alone will be made by the treating clinician in consultation with their patient. Participation in this study will not require any change in the standard clinical care that patients receive.

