Patients recruited to this study will have an effective luminal diameter at the level of the maximal stenosis that is $\leq 50\%$ of that of the distal normal internal carotid artery (i.e. $\geq 50\%$ stenosis). This identification will most commonly be made by duplex sonography, but could be made by any other standard imaging modality namely MRI, angiography, or CT. Our center follows standardized ICAVL-approved (Inter-societal Commission for Accreditation of Vascular Laboratories¹⁰⁰) Doppler velocity criteria to determine the degree of stenosis¹⁰¹; as has been done in previous NIH carotid trials¹⁻⁴.

Exclusion criteria will be a previous stroke or TIA, severe medical illness that would interfere with evaluation of outcomes or reduce the likelihood of a 2-year follow-up, carotid occlusion, and patients scheduled for carotid revascularization procedures. We chose not to use a dementia-screening tool to exclude patients since false positives may be as high as 61%¹⁰².

Exit/Endpoints: Patients will exit the study if they develop a stroke or TIA during follow-up, or if they undergo carotid revascularization; however, data accrued up to the exit point will be included for analysis (see statistical analysis section). Patients will be dropped from the study if the first 3D B-mode imaging assessment as part of the study indicates that their arterial diameter reduction is actually less than 40%.

Specific Aim 2 (a through d) is designed to identify the potential mechanisms of cognitive change in patients with asymptomatic carotid stenosis. Specifically, we will: 1) assess if carotid plaque architecture, plaque composition, microembolic counts, serum pro-inflammatory markers, and cerebral hypoperfusion hypothesized to be in the causal pathway of cognitive decline, could each independently predict a change in cognitive function and 2) assess if patients with asymptomatic carotid stenosis who develop cognitive impairment will differ in these factors compared with similar patients that remain unchanged over 2 years of follow-up. The specific factors that will be analyzed in this aim are: carotid plaque architecture (cross-sectional area, longitudinal sectional area, volume, lipid core volume, core distance from lumen); plaque tissue composition (percent distribution of hemorrhage, lipid, fibro-muscular tissue, and calcium); microembolic counts (on TCD); serum proinflammatory marker levels (hsCRP, MMP-9, IL-6); hemodynamic alteration (cerebrovascular reactivity);

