Additional analysis of Aim 2 focusing on correlations with stroke during follow-up. For the patients in the cohort that suffer a stroke during follow-up, we will have plaque architecture, plaque composition, microembolic count, pro-inflammatory marker, and perfusion information, prior to their stroke. We are aware of the fact that the focus of our study is not on stroke; furthermore, these 5 to 10 patients will be too few to derive statistically strong conclusions. However, we will analyze available data and report additional conclusions on plaque correlates of stroke, if the information is hypothesis-generating.

TCD microembolic counts. We are aware that automated emboli counts and classifications are subject to the effectiveness of signal filtering algorithms. Therefore filters will be programmed according to criteria validated in consensus documents70. As an added precaution, we will analyze all spectral recordings manually to confirm embolic counts.

Temporal consistency. We are aware that the significance of outcomes and interpretation of mechanisms may be influenced by differential temporal effects. While the primary statistical approach will be to evaluate change scores over 2 years; we will describe the temporal pattern of cognitive changes and assess if the hypotheses are temporally consistent at the 1-year time interval.

Vascular risk factor distribution. We realize that the control group will include patients with a heterogeneous mix of one or more vascular risk factors. It is likely that one risk factor may have a larger influence on cognitive function than another; or multiple risk factors together in a patient may influence cognition more than in a patient with one risk factor. However, in a study of this size with finite resources, it will not be possible to expand the control group to the large numbers required to study the effects of each risk factor alone and in various combinations. In any case, that is well beyond the focus of this investigation. We will closely monitor the control subjects to ensure no unusual heterogeneity of cognitive scores. If such is found, we will then focus on recruiting patients with limited (one or two) risk factors alone.

**With regards to the planned additional follow-up, we will perform standard correlation analyses between cognitive scores of the subjects obtained previously with physical function scores that we plan to obtain during the additional follow-up.

ID: VIEW4E02806052800

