Control subjects to be recruited will have no carotid arterial stenosis but will have one or more stroke risk factors. Inclusion criteria will be based on those utilized by the Framingham Study12 13and include: hypertension, defined as $\geq 160/95$ recorded as the average of 2 measurements, or use of an antihypertensive drug; current smoking; diabetes mellitus defined as a random blood glucose of ≥ 126 mg/dL, a previous diagnosis of diabetes, or using hypoglycemic medication or insulin; and previous cardiovascular disease, including coronary heart disease, heart failure, atrial fibrillation, and peripheral arterial disease. Potential subjects with the risk factor/s will undergo duplex ultrasound (DUS) examination to confirm absence of carotid stenosis prior to recruitment to the study. While absence of carotid stenosis will be confirmed most commonly by DUS, alternate imaging modalities (MRA, CTA) if already performed on a patient during the course of their normal clinical management will be acceptable.

Potential risks. The current study does not influence the management of recruited patients. Once a decision has been made that they do not require revascularization, these patients will be recruited to our proposed study. The decision as to whether a subject is appropriate to be followed with medical management alone be made by the treating clinician in consultation with their patient. Participation in this study will not require any change in the standard clinical care that patients receive.

The specific procedures that patients will be subjected to as a result of enrollment in the study, and their potential risks are as follows. 1) Cognitive testing: there are no significant risks to the subjects, except for the psychological burden of being tested for 50 minutes. If at any time the patient reports uneasiness, or symptoms of depression the test will be discontinued and the patient will be given a break. Questionnaires and interviews will be conducted after adequate explanation and reassurance to allay anxiety or concern. If the patient continues to feel anxiety or distress the neuropsychologist will provide support and will offer a treatment referral to a clinical neuropsychologist if necessary.

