1 * Type of data safety monitoring plan for the study:
Data Safety Monitoring by an Individual

ID: VIEW4E1B00E30D400
Name: v2_Monitoring Plan Selection

View: v2_Monitoring Plan - Individual

Monitoring Plan - Individual

You indicated that the monitoring will be done by an Individual.

1 * Identify the individual who will be performing the safety monitoring:
. [name] MD

2 * Describe this individual's role in relation to the protocol:
Principal Investigator

3 * What data will be reviewed?
Adverse Events
Enrollment Numbers
Patient Charts/Clinical Summaries
Laboratory Tests
Raw Data
Outcomes (Primary, Secondary)
Preliminary Analyses

3.1 If Other, specify:

4 * What will be the frequency of the review?
Bi-Annually

4.1 If Other, specify:

5 * Safety monitoring results will be reported to:
IRB

5.1 If Other, specify:

ID: VIEW4E1B026A2A400
Name: v2_Monitoring Plan - Individual

View: v2_Research Related Costs

Research-Related Costs

1 * Is the study's financial supporter (e.g., commercial sponsor, federal or state grant or contract, private foundation, physician-sponsor) covering any research-related costs?
Yes

1.1 If Yes, check all that apply:

Research-Related Services (personnel costs, tests, supplies, exams, x-rays, or consultations required in the study)

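### A contingent rule could cap vascular risk factors in controls only, and no planned Aim 1 analysis adjusts for vascular risk factors

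*Combined protocol and SAP*

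**What the plan says.** Aim 1 (Justification, Objective, & Research Design, item 2) compares stenosis patients on cognition "compared to age-matched individuals without carotid stenosis but with similar vascular risk factors". The control criteria, under Research Related Risks, set a floor and no ceiling: "Control subjects to be recruited will have no carotid arterial stenosis but will have one or more stroke risk factors".

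The paragraph on vascular risk factor distribution (Sample Size and Data Analysis, item 2) acknowledges that controls will be mixed and that "multiple risk factors together in a patient may influence cognition more than in a patient with one risk factor". It then says: "We will closely monitor the control subjects to ensure no unusual heterogeneity of cognitive scores". The consequence follows: "If such is found, we will then focus on recruiting patients with limited (one or two) risk factors alone". The whole paragraph is about the control group, so the word patients there means controls. It gives no statistic, threshold, timing or decision-maker, and no plan for handling controls recruited before and after a change.

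The stenosis criteria (same research design item, and the Eligibility page) do not limit the number of vascular risk factors. The list opens "Exclusion criteria will be a previous stroke or TIA, severe medical illness that would interfere with evaluation of outcomes" and continues with likelihood of follow-up, carotid occlusion and scheduled revascularization.

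For Aim 1, item 2 of the analysis section plans an analysis of covariance of the composite change score at 2 years, adjusted for baseline cognition. Additional analyses correct for age, education and mood. Baseline cognition is also to be compared between groups without adjustment.

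**The concern.** Aim 1 is a non-randomised comparison. Its credibility rests on the two groups differing in stenosis and being otherwise alike in vascular risk. A control group chosen for similar vascular risk should show the variability that multiple risk factors produce. The rule treats that variability as a fault and responds by admitting only low-burden controls, while stenosis patients may still carry any number of risk factors.

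If the rule operated, early and late controls would come from different populations, and the control group as a whole would carry less vascular burden than its eligibility criteria imply. On the plan's own premise, that would make controls look cognitively better for reasons unrelated to stenosis. Because vascular risk factors appear in none of the Aim 1 models, nothing planned would detect or remove the imbalance.

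**Working it through.** **1. Does any planned analysis absorb the imbalance?**

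| Aim 1 analysis | Adjusts for | Vascular risk factors? |
|---|---|---|
| 2-year change score | Baseline cognition | No |
| Additional change-score analyses | Age, education, mood | No |
| Baseline cognition, patients v controls | Nothing (simple comparison) | No |

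The plan also confirms the group distribution of demographic variables. That is a description, not an adjustment.

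**2. Which analyses are exposed?** The unadjusted baseline comparison is exposed directly: any effect of risk burden on the level of cognition goes straight into the group difference. The 2-year change is exposed only if burden affects the rate of decline, since adjustment for baseline score absorbs part of a pure level difference.

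**3. The plan's power figure.** Inputs: 142 per group and 0.4 SD with 90% power (Sample Size and Data Analysis). Alpha is not stated for Aim 1, so two-sided 0.05 is assumed. The noncentrality is 0.4 × √(142/2) = 3.37 on 282 degrees of freedom, which gives power of 91.9%. The 90% claim reproduces. The companion claim of 0.3 SD with 80% power does not (about 71% two-sided), but this point does not depend on it.

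**4. Size of a possible bias.** The documents give neither the risk-factor distribution nor an effect per factor, so every input here is an assumption:

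- Share of controls recruited after the switch: f = 0.5.
- Extra worsening in 2-year change per risk factor: e = 0.1 to 0.2 SD.
- Average reduction r in risk-factor count among late controls, counting the four categories listed under Research Related Risks (hypertension, diabetes, prior cardiovascular disease, smoking):
  - Even spread over 1 to 4: the mean falls from 2.5 to 1.5, so r = 1.0.
  - A 30/40/20/10% split: the mean before is 0.3 + 0.8 + 0.6 + 0.4 = 2.1; the mean after is (0.3 + 0.8)/0.7 = 1.57; so r = 0.53.

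Bias b = f × r × e:

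- Lowest: 0.5 × 0.53 × 0.1 = 0.026, about 0.03 SD.
- Highest: 0.5 × 1.0 × 0.2 = 0.10 SD.

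With a true stenosis effect of zero, the rejection probability comes from the noncentral t distribution with noncentrality b × √71:

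| b (SD) | Noncentrality | Two-sided rejection | Toward a stenosis effect |
|---|---|---|---|
| 0 | 0 | 5.0% | 2.5% |
| 0.03 | 0.25 | 5.7% | 4.4% |
| 0.05 | 0.42 | 7.0% | 6.2% |
| 0.10 | 0.84 | 13.4% | 13.1% |

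A bias of 0.10 SD is a quarter of the 0.4 SD design difference (0.10/0.4 = 0.25).

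**The case against.** Several stronger readings are tempting, and the documents do not support them.

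- *Control recruitment was changed.* The rule is conditional and speaks of a focus. Nothing in the documents shows that it was used.
- *The trigger is the primary outcome.* The primary outcome is the 2-year change score compared between groups. The trigger is the spread of scores within controls. With a 2-year recruitment period, the scores visible during recruitment would be mostly baseline, with some 1-year values. The instrument is the same; the quantity is not.
- *This is selection on the outcome.* No one is admitted or refused on their own score. Later controls would be selected on a baseline covariate, which is a confounding problem that adjustment can address.
- *The bias certainly favours a stenosis effect.* The plan says only that multiple risk factors may influence cognition more, and says nothing on the rate of decline. Neither group's risk-factor distribution is given, so a cap cannot be shown to pull controls away from the stenosis group.
- *The error could reach about 39%.* That needs a shift of 0.20 SD, for instance with nearly all controls recruited under the cap at 0.2 SD per factor. The rule can start only after enough controls have been tested to show heterogeneity, so that scenario contradicts its own trigger.
- *The principal investigator could steer the comparison.* It is stated that "The PI will oversee recruitment of potential participants, collection and storage of study data, regulatory deadlines and data analysis", and the monitoring checklist lists "Preliminary Analyses". But the rule names no decision-maker, and the checklist does not say that results are seen by group. Monitoring access is a separate question.

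These objections limit the claim. What they leave standing is an undefined, control-only cap that conflicts with Aim 1's comparability requirement, with no vascular-risk adjustment planned.

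**Conclusion.** The point holds in a limited form. The plan permits a restriction on controls that works against its own comparability requirement, and no planned Aim 1 analysis would correct the result. Bias toward a stenosis effect is possible. It requires that the rule was used, that it left controls with less vascular burden than stenosis patients, and that burden affects cognition (for the 2-year change, the rate of decline). The unadjusted baseline comparison is the more exposed of the two.

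The illustrative size is 0.03 to 0.10 SD, or a two-sided error of about 6% to 13% in place of 5%. That range rests wholly on the assumed share of controls affected, reduction in count and effect per factor; the documents fix none of them. This should be fixed, as a cheap improvement. It does not by itself invalidate Aim 1.

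**What to change.** Recruitment is recorded as closed (VA-Specific Criteria, item 2.1), so deleting the sentence would not change who was enrolled and would remove the record of a rule that may have operated. Instead:

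1. State whether the rule was applied and, if so, when, on what evidence and by whom.
2. Tabulate the number and type of vascular risk factors by group and by recruitment period.
3. Add the number (or type) of vascular risk factors as a covariate in the Aim 1 model and in the baseline comparison.
4. If the rule was used, add a sensitivity analysis restricted to controls recruited before the switch, or with controls weighted to the stenosis group's risk-factor count.
5. If recruitment reopens, withdraw the rule and keep the control criteria under Research Related Risks throughout.

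The cost is a little more analysis, a few degrees of freedom, and lower precision in the restricted analysis. One practical check is needed: Study Procedures, item 1, describes a baseline vascular risk profile for each patient, whereas control eligibility needs only one qualifying factor. The team should confirm that full counts were recorded for controls, and complete them from existing records where they were not.

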5.1 If Yes, what procedures are in place to assure safety?

N/A

ID: VIEW4E09460F5EC00
Name: v2_Surveys/Questionnaires

View: v2_Testing

Testing

You indicated that this study involves neuropsychological or psychophysiological testing.

If you uploaded a separate research protocol document in the 'Research Protocol' page, cite the applicable section and page numbers from that document in the answer boxes below.

1 * List all of the tests to be used in the study, including both standardized and non-standardized assessments:
 Original ACCOF protocol: 1. Trail making test A & B, 2. Animal naming test, 3. Digit span, 4. Digit symbol coding, 5. Boston Naming Test - short form, 6. Hopkins Verbal Learning Test, 7. COWA oral word association test, 8. Rey Figure Copy, 9. Brief Visuospatial Memory Test, 10. Grooved Pegboard (Affected hand), Grooved Pegboard (Unaffected Hand)

** With regards to the planned additional follow-up: 1) Timed Up and Go, 2) Four Square Step Test, 3) Berg Balance Scale, 4) Dynamic Gait Index, 5) Short Physical Performance Battery

2 * Describe procedures related to all testing:

Patients and control subjects will undergo a 50-minute neurocognitive battery at 3 time points: baseline, 1 year, and 2 years after recruitment. Baseline testing will take place within a few days of recruitment. Following the approach of our prelim data #3 for performing cognitive testing in a similar patient population, the battery will consist of 10 standardized neuropsychological tests for multiple cognitive domains selected on the basis of the NIH harmonization standards, our own preliminary data #3, and published experience in patients with carotid stenosis 5-10, 31. All tests have published age-adjusted norms. All participants will undergo all 10 tests. The order of test administration will remain constant for baseline and follow-up evaluations. Tests will be conducted in a quiet room. The order of administration accommodates the delays required for recall intervals and minimizes stimuli interference in memory tasks.

** With regards to the planned additional follow-up, subjects will undergo balance and walking assessments. The Short Physical Performance Battery requires approximately 10 minutes. The BBS, DGI, TUG and FSST test takes an approximate 5 to 10 minutes each for a total estimated test time of 20 to 40 minutes.

3 * Upload relevant testing materials:

Name	Created	Modified Date
ACCOFSPPB_form.docx	6/9/2017 9:27 AM	6/9/2017 9:27 AM
ACCOF SHORT FORM Dynamic Gait Index.doc	6/9/2017 9:27 AM	6/9/2017 9:27 AM
ACCOF SHORT FORM Berg Balance Scale.docx	6/9/2017 9:27 AM	6/9/2017 9:27 AM
ACCOF Four Square Step Test.doc	6/9/2017 9:27 AM	6/9/2017 9:27 AM
ACCOF Data Form_Timed Up and Go.doc	6/9/2017 9:27 AM	6/9/2017 9:27 AM
Animal naming test (neurocognitive testing)	8/9/2010 11:31 AM	8/9/2010 11:31 AM
Neurocognitive tests	8/5/2010 1:05 PM	8/5/2010 1:05 PM

4 * What is the individual duration of each test and what is the entire duration of all tests?

Original ACCOF protocol: Neurocognitive tests will take 50 mins to complete

** With regards to the planned additional follow-up, the Short Physical Performance Battery requires approximately 10 minutes. The BBS, DGI, TUG and FSST test takes an approximate 5 to 10 minutes each for a total estimated test time of 20 to 40 minutes.

5 * Are any of the questions likely to cause discomfort in participants or cause harm if their confidentiality were breached? (i.e., Illegal activities)

Yes No

6 * Do any questions elicit information related to the potential for harm to self or others?

Yes No

